In contrast to cancer, which is characterized by multiple genetic aberrations, a single activating mutation has been identified in both PROS and PS. In general, clinical presentation is characterized by a mosaic distribution, sporadic occurrence, progressive course of the overgrowth lesions that can affect any tissue or organ in the human body (connective tissue or bone hyperplasia, vascular malformation, etc.). Onset usually occurs at birth or early in life (the first 6-18 months of life). Affected areas generally keep growing throughout the life, but at a slower pace after the patient reaches their third decade of life [Keppler-Noreuil KM, Rios JJ, Parker VE, Semple RK, Lindhurst MJ 2015] [Martinez-Lopez, A., et al 2017] [Biesecker, L. G. 2019]. Currently there is no drug therapy for PROS or PS; the treatment consists of symptom management, mainly surgical management of overgrowth lesions, that ultimately leads to severe physical disabilities with unsatisfactory QoL. The potential to modify and control disease progression is greatest during the rapid disease progression stage which occurs in early childhood. Later treatment may be beneficial, but it will likely have a limited effect.

Miransertib is a novel, potent, and selective allosteric pan-AKT inhibitor with activity against both the active and inactive forms of AKT. AKT1, 2, and 3 are inhibited with IC50 values of 5.0, 4.5, and 16 nM, respectively. Biochemical and cellular analysis showed that miransertib inhibited AKT activation not only by dephosphorylating the membrane associated active form of AKT but also by preventing the inactive form from localizing into the plasma membrane [Yu Y, Savage RE, Eathiraj S, Meade J, Wick MJ, et al. 2015].

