#### 4.2.1 Discontinuation From Treatment

- Participant experiences, in the opinion of the investigator, an acceleration of the overgrowth disease.
- Miransertib-related clinically significant toxicities that do not recover despite optimal treatment or dose reduction.
- Participant needs to take or elects to take another investigational agent.

• Development of any concurrent medical condition that might preclude or

contraindicate the further administration of miransertib.

- Serious protocol violations such as noncompliance with treatment or required follow-up and evaluation as determined by the investigator.
- Investigator's decision (in agreement with the Sponsor's Medical Monitor or designee).
- Participant, or guardian, refusal of further treatment/withdrawal of consent. Reasons for refusal of further treatment/withdrawal of consent should be noted in that participant's medical record.
- Death.

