Miransertib will be supplied as 5 and 10-mg capsules, which should be taken either 1 hour before or 2 hours after a meal. Capsules should be swallowed whole. The preferred beverage for administration is water. However, in cases where there is a medical problem affecting the participant's ability to swallow (eg, the participant has an enlarged tongue), the capsules can be opened, and the powder contents sprinkled onto a small amount of sweetened semiliquid food (eg, apple sauce, chocolate syrup, or ice cream) and administered in its entirety to the participant. The same type of semiliquid food should be used, if possible, for the duration of the study. Refer to the Pharmacy Manual for specific instructions on opening the capsules. To maximize safety and avoid unnecessary exposure to the drug by caregivers, it is recommended that gloves and a facemask be worn by the caregiver when handling opened capsules and that the gloves and facemask are discarded along with the empty capsule shells after use. Pregnant women should not open the capsules.

Miransertib will be administered once daily. Dose will be calculated based on BSA, and actual dose level will be rounded to the nearest 5 mg using a dosing nomogram (Appendix 2). Miransertib will be capped at a BSA >1.77 m^2. During site visits, miransertib dosing will be adjusted for changes in BSA according to the dosing nomogram.

Participants and/or their guardians must use the diary card provided to keep a record of daily intake of each dose of miransertib and the method of administration (capsules swallowed whole or opened and swallowed with semiliquid).

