#### 6.5 Dose Modifications

When a drug-related toxicity is observed, dose interruptions and/or reductions in miransertib administration are allowed. In general, once the dose of miransertib has been modified for a participant, all subsequent doses should be administered to that participant at the modified dose level. A drug-related toxicity is any toxicity considered related, probably related, or possibly related to miransertib.

Dose reduction should occur according to Table 5. Guidelines for dose interruptions for drug-related toxicities and hyperglycemia are detailed in Table 6 and Table 7, respectively.

Table 5 Miransertib Dose Reduction Schedule

Administered Dose	Dose Reduction
25 mg/m  qd:	15 mg/m² qd
	10 mg/m² qd
	5 mg/m  qd
15 mg/m  qd (during first 3 cycles)	10 mg/m² qd
	5 mg/m  qd

qd=once per day

Dose reduction is allowed and should be performed per Table 5. If the dose reduction is indicated, the participant should be assigned to the lower dose and it should be agreed on by the investigator and the Sponsor. Dose re-escalation will not be permitted.

Treatment will be permanently discontinued in case of Grade 2 drug-related toxicity that does not recover within 21 days after holding miransertib, or Grade 3 drug-related toxicity at the lowest dose (5 mg/m²), or if another discontinuation criterion listed in the protocol is met.

Table 6 Dose Interruptions/Reductions for Drug-Related Toxicity Except Hyperglycemia

Event Grade (CTCAE)	Action
Grade 1	Continue current dose level.
Grade 2	Withhold miransertib until recovery to Grade 1 or baseline. If recovery occurs within 21 days of holding miransertib, restart miransertib at the same dose level, unless further dose reduction is required.
	If a participant experienced a Grade 2 drug-related toxicity that does not recover within 21 days of holding miransertib at a higher dose level (25 mg/m  or 15 mg/m  ), they will be allowed to reduce the dose to the next lower level once the event has recovered to Grade 1 or baseline.
Grade 3-4	Withhold miransertib until recovery to Grade 1 or baseline. If recovery occurs within 21 days of holding miransertib, restart miransertib at the next lower dose level for subsequent doses, unless further dose reduction is required.
	If recovery occurs after more than 21 days on drug hold, permanently discontinue miransertib.

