Table 7 Dose Modification for Drug-Related Hyperglycemia and Suggested Clinical Treatment and Management of Hyperglycemia

Event Grade (CTCAE)	Miransertib Dose Modification	Suggested Clinical Treatment and Management of Hyperglycemia
Grade 1		Start once per day home glucose monitoring (alternate between before breakfast and dinner, preferably fasting). No treatment needed.
Grade 2	Grade 1 or baseline.  If recovery occurs within 21 days of holding miransertib, restart miransertib	Start home glucose monitoring twice per day (before breakfast and dinner, preferably fasting).  Treat hyperglycemia per the institutional standard of care.
Grade 3 or 4	Withhold miransertib until recovery to Grade 1 or baseline. If recovery occurs within 21 days of holding miransertib, restart miransertib at the next lower dose level for subsequent doses, unless further dose reduction is required. If recovery does not occur within 21 days of drug hold, permanently discontinue miransertib.	Treat hyperglycemia per the institutional standard of care.

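### Table 5 reduces doses to 10 and 5 mg/m², which the nomogram does not cover; with nearest-5-mg rounding, one reduction step leaves the mg dose unchanged at every BSA from 0.33 to 0.82 m²

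*Protocol*

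**What the plan says.** Protocol Section 6.3 sets the dose from BSA: the "actual dose level will be rounded to the nearest 5 mg using a dosing nomogram (Appendix 2"). Capsules are 5 and 10 mg. An opened capsule must be given whole, so no dose below 5 mg is available.

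Table 5 (Section 6.5) reduces 25 mg/m² to 15, then 10, then 5; participants on 15 mg/m² in the first three cycles go to 10, then 5. Appendix 2 tabulates only 15 and 25 mg/m². Its footnote defines the target as dose level times BSA, with those two levels as examples.

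For Grade 3–4 drug-related toxicity that recovers within 21 days, Tables 6 and 7 both say to "restart miransertib at the next lower dose level for subsequent doses, unless further dose reduction is required". For slower recovery, Table 6 says "If recovery occurs after more than 21 days on drug hold, permanently discontinue miransertib" and Table 7 says "If recovery does not occur within 21 days of drug hold, permanently discontinue miransertib". Section 6.5 also stops treatment for "Grade 3 drug-related toxicity at the lowest dose", which it gives as 5 mg/m². When a reduction is indicated, "the participant should be assigned to the lower dose and it should be agreed on by the investigator and the Sponsor".

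Section 3.1.1 admits children to Cohorts 1–3 from age 2 years and BSA 0.33 m²; Annex 1 has the same limits for Part A.

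**The concern.** The reduction ladder is written in mg/m², but the participant takes whole 5-mg units. In a small child the distance between two mg/m² levels can be less than one unit. A step that exists on paper then need not change what is dispensed.

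A child with Grade 3–4 toxicity could satisfy the restart rule while returning to the daily dose that preceded the event. The stop rule is also affected: it is tied to the 5 mg/m² level, which has no dispensable dose in the smallest children.

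There is a lesser reporting consequence. SAP Section 4.4 summarises AEs by dose within cohort, and Section 4.12 counts participants by mg/m² level. If the assigned level is used, some children labelled 10 mg/m² would be receiving clearly more. Safety and tolerability are now the only primary objective.

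**Working it through.** **Inputs.** Rounding rule and capsule strengths: Section 6.3. Ladder: Table 5. Doses at 25 and 15 mg/m²: Appendix 2 rows. Minimum BSA 0.33 m²: Section 3.1.1.

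**Formula.** Dose = (level × BSA) rounded to the nearest 5 mg, on a 0.01 m² grid. Ties go up, as Appendix 2 itself does at BSA 0.50: 15 × 0.50 = 7.5 is given as 10 mg, and 25 × 0.50 = 12.5 as 15 mg.

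**Reproducing Appendix 2.** The formula matches both rows at every grid point up to BSA 1.77, with one exception: at BSA 0.83, 15 × 0.83 = 12.45 rounds to 10 mg, whereas the table gives 15 mg. The tabulated value is used below.

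**Extending to 10 and 5 mg/m².**
- 10 mg/m²: 10 × 0.33 = 3.3 and 10 × 0.74 = 7.4 both round to 5 mg; 10 × 0.75 = 7.5 and 10 × 0.82 = 8.2 both round to 10 mg.
- 5 mg/m²: 5 × 0.33 = 1.65 and 5 × 0.49 = 2.45 both round to 0 mg; 5 × 0.50 = 2.5 and 5 × 0.82 = 4.1 both round to 5 mg.

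| BSA (m²) | 25 mg/m² | 15 mg/m² | 10 mg/m² | 5 mg/m² | Step with no mg change | Lower, non-zero mg doses below the 15 mg/m² dose |
|---|---|---|---|---|---|---|
| 0.33–0.49 | 10 mg | 5 mg | 5 mg | 0 mg | 15 to 10 | 0 |
| 0.50–0.69 | 15 mg | 10 mg | 5 mg | 5 mg | 10 to 5 | 1 |
| 0.70–0.74 | 20 mg | 10 mg | 5 mg | 5 mg | 10 to 5 | 1 |
| 0.75–0.82 | 20 mg | 10 mg | 10 mg | 5 mg | 15 to 10 | 1 |
| 0.83–0.89 | 20 mg | 15 mg | 10 mg | 5 mg | none | 2 |

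From 0.83 upward both steps below 15 mg/m² lower the dose. The 25-to-15 step lowers it everywhere below BSA 2.84; from there both Appendix 2 rows give 45 mg.

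**Actual dose after the ineffective step.**
- BSA 0.33–0.49, nominal 10 mg/m²: 5/0.33 = 15.2 down to 5/0.49 = 10.2 mg/m².
- BSA 0.75–0.82, nominal 10 mg/m²: 10/0.75 = 13.3 down to 10/0.82 = 12.2 mg/m².
- BSA 0.50–0.74, nominal 5 mg/m²: 5/0.50 = 10.0 down to 5/0.74 = 6.8 mg/m².

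**Sensitivity.** With ties rounded down, the only BSA in the range without a same-mg step is exactly 0.50, where 5 mg/m² would round to 0 mg. If the 0 mg result at 0.33–0.49 were raised to one 5-mg capsule, the 10-to-5 step would fail there as well.

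**Secondary point: the BSA cap.** Section 6.3 caps dosing above BSA 1.77 m² without naming a dose level. Read literally at 15 mg/m², 15 × 1.77 = 26.55 gives a 25 mg maximum, yet Appendix 2 gives 30–45 mg from BSA 1.84. At BSA 2.0 that is 25 mg (25/2.0 = 12.5 mg/m²) against 30 mg (15.0 mg/m²). At 25 mg/m², 25 × 1.77 = 44.25 rounds to 45 mg, so a 45-mg ceiling is a plausible intention.

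**The case against.** The arithmetic is not in dispute. The strongest reply is that the protocol already allows a sensible answer. Reductions go to a lower dose agreed by investigator and sponsor, and re-dispensing the same capsule is hard to call lower. Section 2.2 allows lower doses after early toxicity without tying them to one step. Tables 6 and 7 permit a further reduction, and Section 4.2.1 stops treatment for "Miransertib-related clinically significant toxicities that do not recover despite optimal treatment or dose reduction". The Appendix 2 footnote lets the missing levels be calculated.

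These provisions permit a real reduction but do not require one. Section 6.5 uses dose and dose level interchangeably, and none of the provisions gives a mg figure. The footnote calculation is what produces the unchanged doses.

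The second reply is that the range mixes unequal situations, and this stands. At 0.50–0.74 only the last step fails, so a child must already have been reduced to 10 mg/m². The first step below 15 mg/m² fails only at 0.75–0.82 and at 0.33–0.49; the latter lies below the 0.5 m² that Appendix 2 gives as a 2-year-old's average. Near BSA 0.49, 5 mg is already close to 10 mg/m². The first reduction from 25 mg/m² works throughout the affected range, and exposure after a failed step stays well under the permitted 25 mg/m².

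The cap point is minor: both Appendix 2 rows end at 45 mg, which supports that reading.

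**Conclusion.** The concern holds. Under the protocol's own rounding rule, exactly one Table 5 step leaves the mg dose unchanged at every BSA from 0.33 to 0.82 m², and the 5 mg/m² level has no dispensable dose below 0.50 m². Of the two reductions offered below 15 mg/m², the number giving a lower, non-zero dose is none at 0.33–0.49, one at 0.50–0.82 and two from 0.83.

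This rests on the Appendix 2 rows for 15 and 25 mg/m², nearest-5-mg rounding with ties up for 10 and 5 mg/m², and no assumed minimum dose. The Pharmacy Manual cited in Section 6.3 was not available. The consequence is re-exposure at a dose that has just been followed by Grade 3–4 toxicity, limited by the 21-day rule and sponsor agreement. It should be corrected. The cap wording is a secondary clarification.

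**What to change.** 1. Add two rows to Appendix 2.
   - 10 mg/m²: 5 mg at BSA 0.33–0.74, 10 mg at 0.75–1.24, 15 mg at 1.25–1.74, 20 mg from 1.75.
   - 5 mg/m²: no available dose at 0.33–0.49, 5 mg at 0.50–1.49, 10 mg from 1.50.
   - The top bins assume the BSA cap applies at these levels.
2. Add to Section 6.5: *A reduction must lower the mg/day dose. If the next Table 5 level gives the same mg/day, move to the next level that is lower in mg/day.*
3. State what happens to a participant already on 5 mg/day who needs a reduction: discontinue, or continue by documented investigator–sponsor agreement.
4. In Section 6.3, restate the cap as a 45 mg/day maximum or limit it to 25 mg/m²; alternatively, end the 15 mg/m² row at 25 mg.

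The cost in text is two rows, a short rule and one clause, with no change to data collection or the SAP. The clinical cost depends on item 3. If discontinuation is chosen, a child at BSA 0.33–0.49 would stop after one Grade 3 event at the 15 mg/m² starting dose, and a child at 0.50–0.74 after Grade 3 at nominal 10 rather than 5 mg/m². At 0.75–0.82 the skip rule halves the dose, from 10 to 5 mg, at the first reduction from 15 mg/m². Section 1 states "Currently there is no drug therapy for PROS or PS", so continuing by documented agreement is a reasonable alternative.

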# 2. Cohort 1 (PROS) specific criteria

- Male or female participants ≥2 years and ≤30 years of age with BSA of ≥0.33 m^2.
   Participants should meet the age criterion by/on the date of the first dose Cycle 1 Day 1.
- Have clinical diagnosis of PROS per Diagnostic Criteria for PROS (Appendix 1) and documented somatic PIK3CA variant.
- Have at least one lesion that can be accurately measured by study-standardized volumetric MRI (eligibility to be confirmed by blinded central imaging review).

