## APPENDIX 2 DOSING NOMOGRAM

	15 mg/m² Dose Level									
BSA range (m  )	0.33-0.49	0.5- 0.82	0.83- 1.16	1.17- 1.49	1.50- 1.83	1.84- 2.16	2.17- 2.49	2.50- 2.83	≥2.84	
Target range (mg/day)	4.95-7.35	7.5- 12.3	12.45- 17.40	17.55- 22.35	22.50- 27.45	27.60- 32.40	32.55- 37.35	37.50- 42.45	≥42.60	
Actual Dose (mg qd)	5	10	15	20	25	30	35	40	45	
			25	mg/m  D	ose Leve	l				
BSA range (m  )	0.33-0.49	0.5	-0.69	0.70- 0.89	0.90- 1.09	1.1-1.29	1.30- 1.49	1.50- 1.69	≥1.70	
Target range (mg/day)	8.25- 12.25	12.5	-17.25	17.5- 22.25	22.5- 27.25	27.5- 32.25	32.5- 37.25	37.5- 42.25	≥42.5	
Actual Dose (mg qd)	10		15	20	25	30	35	40	45	

Target mg/day range = Desired dose level (eg,  $15 \text{ mg/m}^2 \text{ or } 25 \text{ mg/m}^2$ ) x BSA range (m^2)

Actual mg/m^2 dose range = Actual dose (mg) / BSA range(m^2)

Generally, a child of BSA  $0.5~m^2$  (the average BSA for a 2-year-old child) should receive 1/4 to 1/3 the dose in mg of that of an adult of BSA  $\sim 1.7~m^2$ . Hence, if the adult gets a 40-mg dose, the child should get a 10-mg dose.

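### At every BSA from 0.33 to 0.82 m², at least one dose-reduction step at or below 15 mg/m² leaves the milligram dose unchanged, so a restart after Grade 3-4 toxicity can be at the same dose

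*Protocol*

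**What the plan says.** Protocol section 6.3 provides 5- and 10-mg capsules, taken once daily, with the dose calculated from BSA; the "actual dose level will be rounded to the nearest 5 mg using a dosing nomogram (Appendix 2"). Appendix 2 tabulates milligrams by BSA band for 15 and 25 mg/m² only. It also defines what is delivered: the mg/m² "dose range = Actual dose (mg) / BSA range".

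Eligibility starts at a small body size. The Cohort 1 criterion is "Male or female participants ≥2 years and ≤30 years of age with BSA of ≥0.33 m"², and Cohorts 2 and 3 and Part A use the same BSA minimum.

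Table 5 in section 6.5 lists reductions from 25 to 15, 10 and 5 mg/m², and from 15 to 10 and 5 mg/m², with no BSA limit. The intent is plain: "If the dose reduction is indicated, the participant should be assigned to the lower dose". After Grade 3-4 toxicity that recovers within 21 days of the hold, Tables 6 and 7 direct the site to "restart miransertib at the next lower dose level for subsequent doses", "unless further dose reduction is required". For late-recovering Grade 2 toxicity at 25 or 15 mg/m², Table 6 says of participants that "they will be allowed to reduce the dose to the next lower level". Section 6.5 permanently stops treatment for "Grade 3 drug-related toxicity at the lowest dose (5 mg/m²").

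**The concern.** The reduction rules are written in mg/m² labels, but the child swallows whole 5- or 10-mg capsules. In a small child, 5 mg is a large fraction of the dose, so two adjacent labels can round to the same capsule count. The label then falls and the exposure does not.

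This matters most after a Grade 3-4 drug-related toxicity, where the reduced restart is the protocol's main protection. It also matters for the stop rule, which is tied to the 5 mg/m² label: at the smallest body sizes, that label has no clear milligram meaning. Such children are within the intended population. Appendix 2 begins at 0.33 m² and gives 0.5 m² as the average BSA of a 2-year-old, and 2 years is the minimum age for Cohorts 1 to 3.

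**Working it through.** **Inputs.** Capsule sizes, once-daily dosing and rounding: section 6.3. Milligrams at 25 and 15 mg/m²: read from Appendix 2. Reduction levels: Table 5. Minimum BSA of 0.33 m²: section 3.1.1.

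**Formula.** Target (mg) = level (mg/m²) × BSA (m²), rounded to the nearest 5 mg.

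**Reproducing Appendix 2.** The table rounds halves up: at BSA 0.50, 15 × 0.50 = 7.5 is given as 10 mg and 25 × 0.50 = 12.5 as 15 mg. In steps of 0.01 m² (to 3.00 m² at 15 mg/m² and 1.77 m² at 25 mg/m²), halves-up rounding matches every tabulated dose but one: BSA 0.83 at 15 mg/m², where the target is 12.45 mg and the table prints 15. Rounding halves down disagrees at 11 values. Halves-up is therefore the table's own convention, and it is used below for the two levels that have no row.

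**Milligrams by level** (unrounded targets in brackets where Appendix 2 has no row):

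| BSA (m²) | 25 mg/m² | 15 mg/m² | 10 mg/m² | 5 mg/m² | Unchanged step |
|---|---|---|---|---|---|
| 0.33-0.49 | 10 | 5 | 5 (3.3-4.9) | 0 or 5 (1.65-2.45) | 15→10; also 10→5 if one capsule is given |
| 0.50-0.69 | 15 | 10 | 5 (5.0-6.9) | 5 (2.5-3.45) | 10→5 |
| 0.70-0.74 | 20 | 10 | 5 (7.0-7.4) | 5 (3.5-3.7) | 10→5 |
| 0.75-0.82 | 20 | 10 | 10 (7.5-8.2) | 5 (3.75-4.1) | 15→10 |
| 0.83-0.89 | 20 | 15 | 10 (8.3-8.9) | 5 (4.15-4.45) | none |

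**Extent.** On the 0.01 m² grid, all 17 + 25 + 8 = 50 points from 0.33 to 0.82 have at least one unchanged step. None of the 107 points from 0.83 to 1.89 has one. The 25→15 step always lowers the dose; in these bands the cut is 10→5 (50%), 15→10 (33%) or 20→10 mg (50%).

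**Delivered dose after the unchanged step** (milligrams / BSA):

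- 0.33-0.49, labelled 10 mg/m²: 5/0.49 to 5/0.33 = 10.2 to 15.2 mg/m².
- 0.50-0.74, labelled 5 mg/m²: 5/0.74 to 5/0.50 = 6.8 to 10.0 mg/m².
- 0.75-0.82, labelled 10 mg/m²: 10/0.82 to 10/0.75 = 12.2 to 13.3 mg/m².

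**The 0.33-0.49 m² band.** There are two readings. Literal rounding of 1.65-2.45 mg gives 0 mg: one step is unchanged, and the 5 mg/m² level named in the stop rule is no drug. If the minimum is one capsule, the child takes 5 mg at labels 15, 10 and 5: both steps are unchanged, and two successive recovered Grade 3-4 events could each be followed by a same-dose restart before the stop rule applies. The protocol does not choose between them.

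**The case against.** The protocol has real safeguards. Drug is withheld until recovery to Grade 1 or baseline. Investigator and sponsor must agree each reduction, and an unchanged capsule count should be visible to both. Tables 6 and 7 leave room for a further reduction, which at 0.75-0.82 m² gives access to 5 mg. Section 4.2.1 separately ends treatment for significant related toxicities that do not recover. The delivered dose after an unchanged step is at most about 15 mg/m², and section 6.3 reports that 15 mg/m² for at least 3 cycles was judged safe. BSA is rechecked at visits, and the lowest band is below the average for a 2-year-old.

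All of that stands, and it bounds the harm. It does not close the gap. The safeguards depend on someone noticing the unchanged step, and they supply no lower dose for a child already on 5 mg. A general judgement that 15 mg/m² is safe says little about a child who has just had a Grade 3-4 reaction on that same capsule dose.

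A reader might go further and infer that exactly one step is empty throughout, or that the Grade 3 stop rule can never apply at 0.33-0.49 m². The documents do not support either. Both need the 5 mg/m² level to mean 0 mg there. No section says so, and Table 5 lists 5 mg/m² as a level for every participant. With a one-capsule minimum, two steps are empty and the stop rule does apply at that label. Nor does the delivered dose rise at an unchanged step: at 0.33 m² it is 15.2 mg/m² both before and after.

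**Conclusion.** The point holds. Under the section 6.3 rounding rule, at least one Table 5 step at or below 15 mg/m² gives no milligram decrease at every BSA from 0.33 to 0.82 m², so a restart after recovered Grade 3-4 toxicity can be at the same dose. At 0.33-0.49 m² the meaning of the 5 mg/m² level is unstated, and either reading leaves a rule that fails: a stop rule that refers to no drug, or two reductions that reduce nothing.

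At 0.50-0.82 m² the result rests on applying Appendix 2's own rounding convention to levels that it does not tabulate. The upper edge of 0.82 rests on the printed 15 mg at BSA 0.83. At 0.33-0.49 m² only the 15→10 step is certain to be unchanged. The documents do not give the number of participants in these bands, so no claim about how many children are affected is possible. This should be fixed: it is a bounded paediatric safety gap.

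**What to change.** 1. Add two rows to Appendix 2.
   - 10 mg/m²: BSA 0.33-0.74 = 5 mg; 0.75-1.24 = 10 mg; 1.25-1.74 = 15 mg; 1.75 and above = 20 mg, subject to the BSA cap.
   - 5 mg/m²: BSA 0.33-0.49 = no dispensable dose below 5 mg; 0.50-1.49 = 5 mg; 1.50 and above = 10 mg.
2. In section 6.5 and Tables 6 and 7, including the Grade 2 late-recovery row, define the next lower dose level as the next Table 5 level that gives fewer milligrams at the participant's BSA. At 0.75-0.82 m² a child on 10 mg would then go directly to 5 mg.
3. State what happens when no lower dose exists, and tie the Grade 3 stop rule to the lowest nomogram dose for that BSA. The sponsor should choose between discontinuation and a reduced regimen written into the protocol and justified for children.

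The drafting cost is two table rows, one definition and a short rule. The clinical cost is larger and should be weighed openly. At 0.33-0.49 m², where 5 mg is also the 15 mg/m² starting dose, a first Grade 3 event at that dose could end treatment unless a reduced regimen is written. At 0.50-0.74 m² one same-dose restart is lost. Section 1 places the greatest potential for disease control in early childhood, which is why item 3 leaves that choice to the sponsor.
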